2.7 DATA MANAGEMENT

The data will be collected by using a web based electronic Case Report Form (eCRF) which will be prepared on the basis of the flow chart included in Section 2.5. The data entry will be performed at site by the Investigator or a designee. The data will be cleared according to specific procedures by the Data Management team of the eCRF provider. The query flow will involve both the monitoring team and the Investigators.

All the details relevant to the data management will be described in the Data Management Plan, which will be prepared by the Data Manager in charge of the study.

2.8 STATISTICAL CONSIDERATIONS

2.8.1 SAMPLE SIZE

In order to detect a 30% difference, in a cross-over design, between the proportion of improved patients in the two groups, with an $\alpha=0.05$ and a power of 80%, a sample size of $N=40$ is required.

2.8.2 DATA ANALYSIS

The sample will be described in its clinical and demographic features using descriptive statistics techniques. Quantitative variables will be described using the following measures: minimum, maximum, range, mean and standard deviation. Qualitative variables will be summarized with absolute and percentage frequency tables. Normality of continuous variables will be checked using Kolmogorov-Smirnov test.

The primary objective will be achieved using descriptive statistics techniques, summarizing questionnaires' results at the planned timepoints. Efficacy will be investigated considering an ANOVA mixed model. Adverse events will be described numerically (absolute frequency by type) and qualitatively. Comparison between the two groups in terms of adverse events will be done with a Chi-square test.

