1.5 EXPERIMENTAL DESIGN

The study will be conducted as a double-blind randomized clinical trial (RCT) and foresees a crossover design, so the population will be divided into two groups, receiving both the medical device and the placebo. The interventions will be described in paragraph 2.3.

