2.2 WITHDRAWAL PROCEDURES

The intervention will be stopped in any case of reported adverse event that can be attributed to GUM Hydral, or in case the patients will need a drug or a medication which could interfere with the xerostomia symptoms.

In order to improve the adherence of the patients to the protocol interventions, all the patients will be asked to update a diary card reporting the usage of the product.

During the duration of the treatment, the patients will be asked not to use any product analogue of Hydral.

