2.3 INTERVENTIONS

The patients will be recruited in the Oral Medicine Department, in a 12 months period.

Study design (see flow-chart)

A baseline visit (T_0) will be conducted three months after the end of RT.

The investigational product GUM Hydral and the placebo will be each administered for a 30-days treatment period.

The patients will be divided into two groups: at **day 1 (baseline - T_0)**, group A will receive treatment product, group B will receive a placebo.

At **day 15**, the compliance of the patient and any adverse effect will be evaluated by a phone call.

At **day 30**, the administration of the products will be stopped, and a 30 days washout phase will take part, followed by Phase 2 of the study.

At **day 61**, each group will be treated with the alternative product.

At **day 75**, the compliance of the patient and any adverse effect will be evaluated by a phone call.

At **day 90**, the final questionnaire will be administered, and the investigation of all endpoints will take place.

Each Visit is described in the following flow-chart

Activities/Procedures	Screening Visit (after 3 months from the end of the RT) From Day-3 to Day 0	Baseline Visit Day 1	DAY 15 (± 2 gg)	DAY 30 (± 7 gg)	DAY 31-60 Washout phase	DAY 61	DAY 75	DAY 90 (End of Study Visit) (± 7 gg)
	PHASE A					PHASE B		
Visit	V1	V2	V3	V4	V5 (Note 2)		V6	V7
Informed Consent signature	X							
Inclusion/Exclusion Criteria verification	X							
Randomization		X						
Demography	X							
Medical and surgical history and underlying diseases	X							
Previous and concomitant treatments	X	X		X	X	X		X
Physical examinations	X			X		X		X
Salivary flow measurement	X			X		X		X
Oral swab for mycetes determination	X					X		X
Medical Device administration and accountability (pts compliance to treatment is assessed at each protocol visit) (Note 3)		X (Note 4)	X	X		X (Note 5)	X	X
Diary card dispensing and verification		X	X	X		X	X	X
QoLs administration	X (Note 6)		X	X		X	X	X
AEs monitoring	X	X	X	X	X		X	X

Note1: the screening visit might have a maximum duration of 1 day

Note 2: during the washout period a telephone contact will be conducted, in order to assess the safety profile of the patients, by specifically asking to refer any AE occurred and relevant concomitant medications administered (if applicable)

Note 3: an instruction procedure to standardize the products administration will be finalized. Patients will be asked to rinse with 15 ml of product, three times a day.

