Note 4: PHASE A, Group A receives Hydral, Group B receives placebo

Note 5: PHASE B, Group A receives placebo, Group B receives Hydral

Note 6: this QoLS administration must be conducted after the ICF signature and before the first Medical Device administration

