2.4.2 SECONDARY OBJECTIVES

- Evaluate Hydral treatment efficacy in reducing xerostomia's symptoms;
- Describe all the adverse events occurred during the study.

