2.6 RANDOMIZATION

Patients will be randomized to treatment groups using sequentially numbered, opaque sealed envelopes (SNOSE). (23)

The principal investigator will be encharged of generating the allocation sequence, of enrolling the participants and of assigning the interventions to the participants.

The co-workers who will administrate the therapies and the patients themselves will be blinded about the selected product.

Only in case of assessment of any adverse event, it will be possible for the P.I. to reveal the product used during the therapy.

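### The adverse-event Chi-square between "the two groups" does not fit the crossover: by sequence it is blind to the product, and by product it ignores that the same patients are counted twice (minor)

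*Combined protocol and SAP*

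**What the plan says.** Section 2.8.2 plans a numerical and qualitative description of adverse events and then one test: "Comparison between the two groups in terms of adverse events will be done with a Chi-square test". It does not define the groups, the period covered, the unit (patients or events) or any pairing. Efficacy, in the same section, is given a mixed model.

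Elsewhere the word has two uses:
- Section 1.5 uses it for the randomised sequences: "so the population will be divided into two groups, receiving both the medical device and the placebo". Section 2.3 follows this; group A starts on Hydral and group B on placebo, and then "PHASE B, Group A receives placebo, Group B receives Hydral".
- Section 2.8.1 sizes the trial on a difference "between the proportion of improved patients in the two groups", which makes sense only as product against product.

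Three other provisions bear on the analysis:
- Events are also collected between the phases: "during the washout period a telephone contact will be conducted, in order to assess the safety profile of the patients" (section 2.3, Note 2). The safety window in section 3.3 runs from consent to the End of Study Visit.
- Section 2.2 says: "The intervention will be stopped in any case of reported adverse event that can be attributed to GUM Hydral". It does not say whether phase B or follow-up is then lost.
- The objective in section 2.4.2 is descriptive: "Describe all the adverse events occurred during the study".

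**The concern.** This is the only statistical comparison of adverse events in the plan. Under the definition of groups used in the design sections, it compares two sets of patients with the same planned exposure. A non-significant result would then say nothing about the product, yet could be reported as no difference in adverse events between groups. Under the by-product reading, the test assumes independent rows although each patient is in both. With the contrast and the handling of pairing left open, the choice could be made after the data are seen, among tests that answer different questions.

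**Working it through.** **Plan's own figure.** None is stated for this test. N=40 in section 2.8.1 concerns efficacy. It cannot be uniquely reproduced, because the discordance rate is not given (two-sided McNemar needs 40 pairs at discordance 0.48, but 24 at 0.30 and 59 at 0.70). It is used below only as the assumed total.

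**Assumptions, not in the documents.** 40 patients, 20 per sequence; event risks pH (Hydral) and pP (placebo) per phase; within-patient correlation phi; no period or carryover effect; two-sided alpha 0.05; uncorrected Chi-square.

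**Reading 1: sequence A against B, whole study.** The chance of at least one event is pH + pP − p11, where p11 = pH·pP + phi·√[pH(1−pH)·pP(1−pP)]. The order of the products does not enter. At 30% and 10% with phi = 0 it is 0.30 + 0.10 − 0.03 = 0.37 in both sequences. The null hypothesis is therefore true despite a threefold product effect. Exact rejection rates are 5.1–5.3% at 20/20, 5.4–5.5% at 16/24 and 5.2–5.4% at 12/28.

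**Reading 2: Hydral against placebo, unpaired.** With equal risks p, the true variance of the difference is 2p(1−p)(1−phi)/n, while the test uses 2p(1−p)/n. Type I error is therefore about 2[1 − Φ(1.96/√(1−phi))].

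| phi | 1.96/√(1−phi) | Approximation | Computed at 20% vs 20% |
|---|---|---|---|
| 0 | 1.96 | 5.0% | 5.0% |
| 0.15 | 2.13 | 3.4% | 3.5% |
| 0.3 | 2.34 | 1.9% | 2.0% |
| 0.5 | 2.77 | 0.6% | 0.7% |

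Exact enumeration gives 5.1%, 3.5%, 2.1% and 0.7%. If N=40 were per group, the last two would be 2.0% and 0.6%.

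**Power by product, 30% vs 10%, unpaired against mid-p McNemar, all pairs complete.** 63% vs 60% (phi 0), 64% vs 66% (0.15), 65% vs 75% (0.3). At 15% vs 5%: 35% vs 27% (phi 0), 31% vs 32% (0.3).

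**Example.** Of 40 patients, 6 have an event on both products, 8 on Hydral only, 1 on placebo only and 25 on neither. Risks are 14/40 and 7/40, a difference of 0.175. The unpaired Chi-square is 3.16 (p = 0.075). McNemar is (8−1)²/9 = 5.44 (p = 0.020; exact 0.039). With patient-clustered standard errors, SE = √[(9 − 49/40)/(40·39)] = 0.0706, so t = 2.48 on 39 df (p = 0.018; 95% CI 0.032 to 0.318).

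**Patients with one period.** Let q be the share of group A patients with a Hydral event who have no phase B data.
- Dropping them favours Hydral. With equal risks of 20%, phi = 0 and q = 1, group A keeps on average 16 patients with no Hydral events and 3.2 placebo events, while group B contributes 4 of each. The complete-pairs difference is −3.2/36 = −8.9 points although the truth is 0. McNemar's null type I error then reaches 10–15% (phi 0.3 to 0).
- At 30% vs 10%, phi 0.15, McNemar power is 55%, 42% and 16% at q = 25%, 50% and 100%; the unpaired test on all exposed patients stays at 64–66%. At q = 50% the estimated difference is 14.9 points on complete pairs and 20.5 with all exposed patients (truth 20.0).
- Keeping them is not free of bias. With equal risks of 20%, phi = 0.3 and q = 1, p11 = 0.04 + 0.3·0.16 = 0.088. Placebo risk among group A patients who continue is (0.20 − 0.088)/0.80 = 0.14, so the overall placebo risk is (16·0.14 + 20·0.20)/36 = 0.173. The difference is +2.7 points, against Hydral.

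**The case against.** The strongest reply is that a sensible analyst would read the sentence by product, as section 2.8.1 does, and that nothing harmful follows. McNemar's test is itself a chi-square test, so a paired reading is open. So is a comparison of A with B in phase A alone, which is valid though weak (36% power at 30% vs 10%, 20/20). The objective is to describe events, the description is planned separately, and the trial was not sized for this test. All of that stands, and it limits the severity. It does not settle what will be done, because the sentence states none of these choices and the design sections define the groups as sequences.

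A reader might infer more than the documents support:
- *That the unpaired test inflates false positives.* Under positive correlation it does the opposite.
- *That it necessarily loses power.* This depends on rates and correlation that are not given; at low values nothing is lost.
- *That events cannot be traced to a product.* The product in each phase is fixed by sequence, and section 2.6 allows unblinding: "Only in case of assessment of any adverse event, it will be possible for the P.I. to reveal the product".
- *That the silence on washout events and one-period patients is an error in itself.* It is missing detail. The events would still appear in the planned description, and section 2.2 does not say that phase B data are lost.
- *That complete-pairs McNemar is the natural replacement.* It discards patients stopped for a Hydral-attributed event if they lack phase B data, and so can be worse than the unpaired test.

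**Conclusion.** The concern holds as a minor point: the sentence is wrong as written for this design. By sequence over the whole study, the test rejects at about 5% whatever the product effect, absent period or carryover effects. By product, an ordinary Chi-square violates independence and is conservative under positive correlation, with type I error falling from 5.0% at phi 0 to 0.7% at phi 0.5 (assumed 20% vs 20%, N=40 in total). The mismatch itself follows from the text and does not depend on these figures; its size rests on assumed event rates and correlations. No effect on the efficacy analysis follows.

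**What to change.** In section 2.8.2, replace the Chi-square sentence with the following.

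- Compare patients with at least one adverse event on Hydral with patients with at least one on placebo, each event being assigned to the product in use at onset.
- Use all patients exposed to each product as its denominator. Report the risk difference with a 95% CI and test from patient-clustered (robust) standard errors, with a small-sample correction (t reference on the number of patients minus one), so that one-period patients stay in.
- List events starting in the washout separately, outside this comparison.
- Report the number of one-period patients by sequence.
- Give McNemar on complete pairs as a sensitivity analysis only.

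This takes a few sentences and no new data. There are two statistical costs. At zero correlation, power is slightly lower than for the unpaired test (60% vs 63% at 30% vs 10%). If many patients with a Hydral event lack phase B data and correlation is high, the estimate is mildly biased against Hydral: null type I error is 6.4% at phi 0.3 and 9.9% at phi 0.5 if every such group A patient lacks it. This is why the one-period counts must be shown.

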3. SAFETY AND TOLERABILITY EVALUATION

3.1 SAFETY AND TOLERABILITY PARAMETERS

Since GUM Hydral is intended for topical use only and its constituents are based on natural products, an evaluation of the vital signs is not necessary. The adverse events will be evaluated.

3.2 LABS PARAMETERS.

Oral swabs for mycetes will be taken in order to assess whether the presence of candida species can modify the perception of xerostomia.

3.3 VIGILANCE ACTIVITIES

DEFINITIONS

INCIDENT

Any malfunction or deterioration in the characteristics and/or performance of a device, as well as any inadequacy in the labeling or the instructions for use which, directly or indirectly, might lead to or might have led to the death of a patient, or USER or of other persons or to a serious deterioration in their state of health.

FATAL INCIDENT

Incident where the Medical Device (MD) determined (or contributed to determine) the patient death (or user death). Factors such as potential risks in use of MD, characteristics of MD, patient health condition, etc. should be considered to assess the causality relationship between the MD and the death. The evaluation of the health professional who witnessed the fatal event should be also taken into account.

INCIDENT THAT HAS CAUSED A SERIOUS DETERIORATION IN THE HEALTH CONDITION

Incident in which the MD has caused a serious deterioration in the health condition of a patient or user or third person is to be intended as:

- an illness or life-threatening injury;
- an impairment of a body function;
- a condition requiring medical or surgical intervention to prevent an impairment of a body function or impairment of a body structure;
- a condition requiring hospitalization or prolongation of hospitalization.

NEAR INCIDENT

Near Incident is to be intended as:

- the condition where any malfunction or deterioration in the characteristics or performances, as well as any inadequacy in the labeling or instructions for use could result, if the MD had been used, a worsening of health condition or death of the patient or user, *or*
- the condition where any malfunction or deterioration in the characteristics or performances, as well as any inadequacy or in the labeling or instructions for use could cause during the procedure of use or following, if health personnel had not intervened, a worsening of health condition or death of the patient or user.

COMPLAINT

Health care professionals should report only to the manufacturer or authorized representative or distributor any non-compliance and / or events that are not listed above, concerning the use or pre-use procedures, related to a MD.

INVESTIGATOR REGULATORY OBLIGATIONS

The Investigator should submit any Incident/Near Incident to the Regulatory Authority (Ministero della Salute, Ufficio VI della Direzione Generale dei Dispositivi Medici e del Servizio Farmaceutico, DGDMF, [contact]), to the EC (by e-mail or fax) and to the manufacturer/ authorized representative/distributor following the timelines indicated in the table herebelow:

REPORT	DEADLINE*
--------	-----------

Incident	Within 10 calendar days from the date of knowledge by the Investigator
Near Incident	Within 30 calendar days from the date of knowledge by the Investigator

** to be applied also for Follow-Up reports and for claims to be reported to manufacturer/ authorized representative/distributor.*

This form must be filled in with all the available information, dated and signed.

Upon request by the Regulatory Authorities, the Investigator must complete his/her report with all available follow-up information.

SAFETY FOLLOW-UP

The safety information will be recorded by the Investigator starting from the date of the Informed Consent signature and will end-up at the End of Study Visit.

4. ETHICAL ISSUES

This trial will be carried out in compliance with the protocol, designed to ensure adherence to Good Clinical Practice, as described in:

- 1 ICH Harmonised Tripartite Guidelines for Good Clinical Practice, 1996. Note for Guidance on Good Clinical Practice CPMP/ICH/135/95
- 2 EU Directive 2001/20/EC, 2005/28/EC
- 3 Declaration of Helsinki (1964, and its amendments and subsequent clarification
- 4 UNI EN ISO 14155:2011

The Principal Investigator agrees, when signing the protocol, to adhere to the instructions and procedures described in it and thereby to adhere to the principles of Good Clinical Practice that it conforms to.

4.1 PROTOCOL AMENDMENTS

All significant deviations from the protocol will be documented. Any changes made after data analysis has begun will be documented as such and the rationale provided.

5. ADMINISTRATIVE PROCEDURES

5.1 ARCHIVING

The Principal Investigator will ensure the archiving of the essential documents of the study as specified by the GCP and in compliance with the applicable legislation. The Principal Investigator will adopt all the necessary measures to avoid accidental or premature destruction.

At the end of the study, all documents relating to the study should be retained for the period required by the applicable local regulatory requirement(s) or longer, if needed by the Sponsor.

6. INVESTIGATOR'S RESPONSIBILITY

The Investigator is aware of his responsibility for all the actions delegated by him/her to other members of his/her staff assigned to the conduct of the study. Except where specifically required. The Investigator is obliged to conduct the study in compliance with the study protocol and in adherence to the Good Clinical Practice (ICH-E6-R1, UNI EN ISO 14155:2011 and with the principles of the Declaration of Helsinki (1964) and successive revisions as well as in respect of the applicable legislation.

